13.3	EVENTS THAT DO NOT REQUIRE REPORTING TO THE SPONSOR	26
13.4	Serious Adverse Events	27
14.0	CLINICAL EVENTS COMMITTEE (CEC)	27
15.0	MEDICAL DEVICE REPORTING	28
15.1	Manufacturer Reporting Requirements	28
16.0	STATISTICAL CONSIDERATIONS	28
16.1	STATISTICAL OVERVIEW	28
16.2	Analysis Populations	28
16.3	SAMPLE SIZE CALCULATIONS AND ASSUMPTIONS	29
16.4	Safety	29
16.5	EFFICACY	30
16.6	Statistical Analyses	30
17.0	QUALITY CONTROL AND QUALITY ASSURANCE	31
17.1	Protocol Deviations	31
17.2	INVESTIGATOR / INVESTIGATIONAL SITE TRAINING	32
17.3	Monitor Training	32
17.4	Study Monitoring	32
17.5	SITE MONITORING	32
17.6	REGULATORY AGENCY INSPECTION	32
18.0	ETHICS/PROTECTION OF HUMAN SUBJECTS	33
18.1	Ethical Standard	33
18.2	Institutional Review Board/Ethics Committee	33

ABLATE	Post-Approval Study	
18.3	INFORMED CONSENT PROCESS	33
18.4	Subject Confidentiality	33
19.0	DATA HANDLING AND RECORD KEEPING	34
19.1	Investigator Records	34
19.2	Investigator Reports	35
19.3	Data Management Responsibilities	36
19.4	Study Records Retention	36
20.0	PROTOCOL AMENDMENTS	36
21.0	TERMINATION OF STUDY OR STUDY SITE PARTICIPCATION	36
22.0	LITERATURE REFERENCES	38
APPEND	IX A: ADVERSE EVENT DEFINITIONS	39

PROTOCOL SUMMARY

Title:

AtriCure Synergy RF Energy Lesions For Non-Paroxysmal Forms Of Atrial Fibrillation Treatment During Concomitant On-Pump Cardiac Surgery Post-Approval Study (or "ABLATE PAS")

Device:

The AtriCure Synergy Ablation System

•

Objective:

The primary objective of this post-approval study is to evaluate clinical outcomes in a cohort of patients treated during commercial use of the AtriCure Synergy Ablation System by physicians performing the Maze IV procedure.

Design:

This prospective, open label, multi-center, observational, single arm registry is designed to monitor the AtriCure Synergy Ablation System continued safety and efficacy during the peri-procedural and long term phase during commercial use in patients being treated for non-paroxysmal forms of atrial fibrillation (AF) who are undergoing a concomitant open, on-pump cardiac surgical procedure.

Primary Efficacy
Outcome:

The proportion of patients free from AF (i.e. no episodes lasting > 30 continuous seconds duration of either Atrial Fibrillation, Atrial Flutter or Atrial Tachycardia) while off Class I and III antiarrhythmic drugs for at least 4 weeks (except amiodarone which must be 12 weeks prior to assessment), as determined by an independent core lab assessment of 48 hour Holter, Zio[™] Patch or PPM interrogation recording performed at a minimum of 12, 24 and 36 months postoperatively (hypothesis test at 36 months).

Primary Safety
Outcome:

[figure not shown]
The proportion of patients with any serious device or ablation procedure-related adverse events
 within 30 days post-procedure or hospital discharge (whichever is later) as adjudicated by a Clinical Events Committee.

Secondary Efficacy Outcome:

The proportion of patients free from AF, regardless of AAD usage (i.e. no episodes lasting > 30 continuous seconds duration of either Atrial Fibrillation, Atrial Flutter or Atrial Tachycardia), as determined by an independent core lab assessment of 48 hour Holter, Zio™ Patch or PPM interrogation recording performed at a minimum of 12, 24 and 36 months postoperatively.

Secondary Safety Outcomes:

- Composite major adverse event: Serious adverse events occurring post-operatively within 30 days post-procedure or hospital discharge (whichever is later) including:
 - Death (includes deaths after 30 days or hospital discharge if death is procedure related).
 - Stroke (resulting in significant permanent disability)
 - o TIA
 - Myocardial infarction, and
 - Excessive bleeding (requiring >2 units of blood replacement and surgical intervention).

 Pacemaker implantation (PPM) within 30 days post procedure will be summarized and reported by reason for PPM (i.e., sinus node dysfunction, AV-node, etc.).

Planned Enrollment:

Up to 390 subjects.

Population:

Subjects who have non-paroxysmal forms of AF and are scheduled to undergo a primary open cardiac surgical procedure requiring cardiopulmonary bypass including valve surgery and/or CABG.

Follow-up Schedule: All patients will undergo clinical follow-up in hospital and at 30 days,

4, 12, 24 and 36 months post procedure.

Number of Sites: 50 study centers located in North America

Study Duration Study Start: Q3/2012

(Estimated): Enrollment Completion: Q4/2014 Follow Up Completion: Q4/2017

Final Report: Q2/2018 (See detail in section 6.5)

Inclusion Criteria:

[figure not shown]
• Age ≥ 18 years.

- Subjects with Persistent or Longstanding Persistent Atrial Fibrillation defined in accordance to HRS AF expert consensus statement (2012)¹
 - Persistent AF is defined as continuous AF that is sustained beyond seven days. Episodes of AF in which a decision is made to electrically or pharmacologically cardiovert the patient after > 48 hours of AF, but prior to 7 days, should also be classified as persistent AF episodes.
 - Longstanding persistent AF is defined as continuous AF of greater than 12 months duration.
 - The performance of a successful cardioversion (sinus rhythm >30 seconds) within 12 months of an ablation procedure with documented early recurrence of AF within 30 days should not alter the classification of AF as long-standing persistent
- Subject is scheduled to undergo elective open cardiac surgical procedure(s) to be performed on cardiopulmonary bypass for one or more of the following: Coronary Artery Bypass Grafting (CABG), Mitral valve repair or replacement, Aortic valve repair or replacement, Tricuspid valve repair or replacement. In conjunction with these procedures Patent Foramen Ovale (PFO) or A Septal Defect (ASD) repair are allowed.
- The patient (or their legally authorized representative) agrees to participate in this study by signing the IRB approved informed consent form.
- Willing and able to return for scheduled follow-up visits.

[figure not shown]
Exclusion Criteria:

- Stand alone AF without indication(s) for concomitant cardiac surgery.
- Need for emergent cardiac surgery (i.e. cardiogenic shock).
- Preoperative need for an intra-aortic balloon pump or intravenous inotropes
- Pregnancy or desire to get pregnant for the duration of the study (concomitant surgical procedure through the thirty six (36) month follow-up period).
- Enrolled in another clinical trial that could confound the results of this study.

Sample Size:

Steering Committee:

1.0 INTRODUCTION: BACKGROUND INFORMATION AND SCIENTIFIC RATIONALE

1.1 Background Clinical Information

Atrial fibrillation (AF) is the most common sustained tachyarrhythmia seen in clinical practice, particularly in the elderly, and is an important risk factor for stroke. AF accounts for 34% of arrhythmias as the principal diagnosis.¹

AF is a condition in which there are highly asynchronous atrial depolarization without effective atrial contraction. AF is also characterized by the presence of rapid, irregularly timed impulses reaching the AV node from the atrium and is associated with irregularly timed ventricular response. The atrial rate can be between 350 to 600 beats per minute. Due to the low pass filtering properties of atrio-ventricular (AV) node, the ventricular response is much slower.

It is estimated that 2.2 to 5.1 million people in the U.S. have AF.^{2,3} The prevalence of AF increases with age. The condition affects fewer than 1% of people under age 60, with nearly 4% of people 60 years and older and 9% of people 80 years and older having been diagnosed with AF.⁴ In 85-95% of cases, the presence of AF is related to the presence of underlying heart disease, left atrial enlargement, or abnormal atrial electrophysiology.

AF can lead to thromboembolism and stroke in approximately 5 -10% of high-risk patients.⁵ Risk increases with age and with the coexistence of structural heart disease, such as mitral regurgitation, which is common in these patients. Because there are no effective atrial contractions, areas of blood stasis are set up in the atria (particularly in the appendages) and clot sometimes forms. In about 5% of patients with AF, clotted blood dislodges from the atria and causes stroke. The American Heart Association estimates that in the United States, AF is responsible for over 70,000 strokes each year. In just the United States, it is estimated that AF accounts for 1.4 million outpatient visits and over 227,000 hospitalizations per year.^{2,3}

2.0 AtriCure System

The trial is designed as a Post Approval Study to investigate the acute and long-term outcomes of the AtriCure Synergy Ablation System. The product has been used in previously clinical IDE trials (RESTORE and ABLATE) that were used to support market approval of the system. The clinical results were presented to the FDA Advisory Panel in October of 2011. This group recommended approval this product. FDA accepted their recommendation and the Synergy Ablation System received approval in December 2011. A condition of this approval is to conduct this Post Approval Study aimed at collecting information on the acute and longer term outcomes on the product when used to complete the MAZE IV procedure in a commercial setting.

3.0 ATRICURE SYNERGY ABLATION SYSTEM LABELING

3.1 Indications for Use

The AtriCure Synergy Ablation System is intended to ablate cardiac tissue for the treatment of persistent atrial fibrillation (sustained beyond seven days, or lasting less than seven days but necessitating pharmacologic or electrical cardioversion) or longstanding persistent atrial fibrillation (continuous atrial fibrillation of greater than 12 months duration) in patients who are undergoing open concomitant coronary artery bypass grafting and/or valve replacement or repair.

3.2 Contraindications

The AtriCure Synergy Ablation System should not be used for contraceptive coagulation of fallopian tubes. The device is not designed for safe and effective use for that purpose.

3.3 Warnings and Precautions

The warnings and precautions can be found in the AtriCure Synergy Ablation System Instructions for Use.

4.0 ATRIAL FIBRILLATION CLASSIFICATION

In an effort to bring uniformity to the various nomenclature being used in the medical community, the Heart Rhythm Society Task Force on Catheter and Surgical Ablation (HRS/EHRA/ECAS) have recommended the following AF classification scheme based upon the patterns of duration and mode of termination¹.

- Paroxysmal AF is defined as recurrent AF (≥2 episodes) that terminates spontaneously within 7 days. Episode of AF ≤48 hours duration that are terminated with electrical or pharmacologic cardioversion should also be classified as paroxysmal AF episodes.
- Persistent AF is defined as continuous AF that is sustained beyond seven days. Episodes of AF in which a decision is made to electrically or pharmacologically cardiovert the patient after >48 hours of AF, but prior to 7 days, should also be classified as persistent AF episodes.
- Longstanding persistent AF is defined as continuous AF of greater than 12 months duration. The
 performance of a successful cardioversion (sinus rhythm >30 seconds) within 12 months of an
 ablation procedure with documented early recurrence of AF with30 days should not alter the
 classification of AF as long-standing persistent.

The ABLATE Post Approval Study (ABLATE PAS) will focus on those patients with non-paroxysmal forms of AF who meet the inclusion/exclusion criteria defined in **Section 9** of this protocol.

5.0 STUDY OBJECTIVE

The primary objective of this ABLATE Post-Approval Study (or "ABLATE PAS") is to evaluate clinical outcomes in a cohort of patients receiving treatment with the AtriCure Synergy Ablation System in performing the Maze IV procedure. The efficacy of the device will be demonstrated by establishing that the device effectively eliminates non-paroxysmal forms of atrial fibrillation. Elimination of non-paroxysmal forms of atrial fibrillation will be assessed by a 48 hour Holter Monitor, Zio™ Patch, or PPM

AtriCure Inc.

CONFIDENTIAL

Rev. M

interrogation after the procedure that demonstrates no signs of atrial fibrillation/atrial flutter/ atrial tachycardia longer than 30 seconds as assessed by an independent core laboratory.

Safety shall be assessed in the study using the incidence of serious device or ablation procedure related adverse events which occur within 30 days post-procedure or hospital discharge (whichever is longer).

6.0 STUDY DESIGN

The ABLATE PAS is a multi-center, prospective, observational study designed to evaluate the AtriCure Synergy Ablation System for continued safety and efficacy during commercial use in a real world settings in patients with non-paroxysmal forms of AF. One of the goals of a post approval study is to assure that the provider and subject population are representative of the general population.

[figure not shown]
_

[figure not shown]
AtriCure Inc. Page 12 of 46

5.2 Study Center Initiation/Start	· IIn
The ARI ATE PAS will utilize the exis	ting subjects and sites currently involved in the ARIATE AF Registry

It is anticipated that at the initiation of ABLATE PAS a total of 75 subjects will be enrolled at the 20

ABLATE AF sites.

[figure not shown]

[figure not shown]

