16.4 Safety

The primary safety objective of the ABLATE Post Approval Study (ABLATE PAS) is to demonstrate that the serious device and ablation procedure related AE rate (excluding pacemaker implantation) within 30 days or prior to discharge (whichever is later) of the AtriCure Synergy Ablation System is no worse than a performance goal derived from the non-paroxysmal AF subject cohort of the combined AtriCure IDE ABLATE and ABLATE AF clinical trials.

The rate of serious device or ablation procedure related adverse events (excluding pacemaker implantation) within 30 days or prior to discharge (whichever is later) in the non-paroxysmal AF subject cohort of the combined AtriCure IDE ABLATE and ABLATE AF clinical trials was 6.25% (4/64).

The acceptable upper limit of the serious device and ablation procedure related AE rate for the ABLATE PAS trial (i.e. the performance goal) is established at 10%.

The primary safety hypotheses for this study are stated as follows:

 $H_0: \pi_{PAS_SAFETY} \ge 10\%$ $H_1: \pi_{PAS_SAFETY} < 10\%$

Using a one-sided exact binomial test for proportions at the 0.05 overall level of significance, a total of 333 subjects are required to demonstrate that the 30 day serious device or procedure related AErate

(excluding pacemaker implantation) in subjects treated with the AtriCure Synergy Ablation System is < 10% (the performance goal) with 80% power. This calculation was completed using PASS 2008 Power and Sample Size Software by NCSS.

A maximum of 15% Loss to Follow-Up (LTFU) is anticipated through 30 days, as such the sample size for enrollment is increased to 390 subjects to ensure a minimum of 333 subjects are available for assessment of the primary safety endpoint through 30 days. Should LTFU be less than 15%, enrollment will stop early given the safety endpoint is powered to at least 80%.

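### The 10% safety goal is derived partly from ABLATE AF subjects, who may also be in the PAS sample tested against it; the overlap should be stated and the safety test repeated without them

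*Combined protocol and SAP*

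**What the plan says.** Section 16.4 sets the primary safety objective as showing that the 30-day rate of serious device- or ablation-related events (pacemaker implants excluded) is no worse than a "performance goal derived from the non-paroxysmal AF subject cohort of the combined AtriCure IDE ABLATE and ABLATE AF clinical trials". It reports that the rate in the "combined AtriCure IDE ABLATE and ABLATE AF clinical trials was 6.25% (4/64"), and the acceptable upper limit ("i.e. the performance goal) is established at 10"%) becomes the null value. The sample size follows: "Using a one-sided exact binomial test for proportions at the 0.05 overall level of significance, a total of 333 subjects are required", for 80% power. Enrollment is raised to 390 because "A maximum of 15% Loss to Follow-Up (LTFU) is anticipated through 30 days".

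The study center initiation text in Section 6.0 says the PAS will use the existing "subjects and sites currently involved in the ARIATE AF Registry", where the odd spelling is a scan error. It continues: "It is anticipated that at the initiation of ABLATE PAS a total of 75 subjects will be enrolled at the 20" ABLATE AF sites. Text around these sentences is missing from the public copy.

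Section 16.2 defines the primary analysis population by receipt of the device for non-paroxysmal AF during concomitant surgery. It does not separate subjects who contributed to the 4/64. Section 16.6 plans one exact binomial test for safety, and its sensitivity analyses deal only with missing data.

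**The concern.** A one-sample test against a performance goal treats the goal as external and every outcome in the sample as still to be observed. Here the plan itself says the goal comes from a cohort that includes ABLATE AF subjects, and ABLATE AF subjects are also brought into the sample. Any subject in both places helps to set the bar and then to clear it, with an outcome already known when the bar was set.

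This is the primary safety conclusion of a study required as a condition of approval (Section 2.0). If part of the evidence repeats the data behind the goal, the result is a less independent confirmation than the test's nominal level suggests. As written, a reader cannot tell how much less.

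**Working it through.** **Inputs.** From Section 16.4: null rate 10%, reference rate 4/64 = 6.25%, one-sided exact binomial test at 0.05, 333 evaluable, 390 enrolled, 15% loss. From Section 16.5: 45 non-paroxysmal IDE ABLATE subjects in the efficacy reference (26/45).

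**Plan's own figure.** The largest c with P(Bin(333, 0.10) ≤ c) ≤ 0.05 is 24.
- Size: P(Bin(333, 0.10) ≤ 24) = 0.0492.
- Power: P(Bin(333, 0.0625) ≤ 24) = 0.801.

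So 333 reproduces, with almost no slack in power.

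**Overlap range (assumption).** The ABLATE AF share of the 64 is not given. If all 45 IDE subjects are among the 64, ABLATE AF contributed at most 64 − 45 = 19. The overlap m is therefore taken as 0 to 19.

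**Error rate given known outcomes.** If m of the 333 are already known and carry k events, the chance of passing at a true rate of 10% is P(Bin(333 − m, 0.10) ≤ 24 − k).

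| m | k=0 | k=1 | k=2 | k=3 | k=4 |
|---|---|---|---|---|---|
| 5 | 5.9% | 3.9% | 2.4% | 1.5% | 0.9% |
| 10 | 7.0% | 4.6% | 3.0% | 1.8% | 1.1% |
| 19 | 9.4% | 6.4% | 4.2% | 2.6% | 1.6% |

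**Average given 4/64.** If the m overlapping subjects are a random draw from the 64, k is hypergeometric (64 subjects, 4 events, m drawn). For m = 19 the weights for k = 0 to 4 are 0.2345, 0.4243, 0.2664, 0.0686 and 0.0061, so the average is

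0.2345 × 0.0937 + 0.4243 × 0.0640 + 0.2664 × 0.0420 + 0.0686 × 0.0264 + 0.0061 × 0.0158 = 0.062.

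The same sum gives 0.053 for m = 5 and 0.056 for m = 10.

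**If 10% is regarded as fixed independently of these data.** Weighting the m = 19 row by Bin(19, 0.10), over all possible k, returns 0.0492. Overlap alone does not move the unconditional size.

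**Power of a test without the overlapping subjects, at the 390 cap.**
- Excluding 19: (390 − 19) × 0.85 = 315 evaluable; critical value 22, size 0.040, power 0.750.
- Excluding 10: (390 − 10) × 0.85 = 323 evaluable; critical value 23, size 0.046, power 0.781.

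**The case against.** The strongest reply is that the hypothesis concerns a stated constant. If 10% is fixed, the size is 4.92% whatever the overlap, and the conditional rates above describe particular event counts rather than the test's type I error. That stands as far as it goes. A reader might infer that the 5% level fails; the documents do not show this. The level can also fall below 5%: with 19 overlapping subjects this happens once they carry two or more of the four events, and with 5 or 10 once they carry one. But Section 16.4 says the goal was derived from this cohort and does not show how 6.25% became 10%, so independence cannot be confirmed either.

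A reader might also treat all 75 subjects anticipated at PAS start as known outcomes and obtain much larger error rates. The documents do not support that. The 75 is a forecast, nothing says their 30-day outcomes were known when the goal was set, and under the bound above at most 19 of them could be among the 64.

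Finally, the Section 6.0 text is incomplete, and Section 16.2 leaves other sub-populations to the statistical analysis plan, so conditions on carrying subjects over may exist out of view. Also, Section 6.0 speaks of a registry and Section 16.4 of clinical trials; treating them as one cohort is an inference from the shared name. These points limit what can be claimed about the size of the overlap. They do not remove the need to state it: the legible parts of Sections 16.2, 16.4 and 16.6, where a separation would belong, contain none.

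**Conclusion.** The primary safety test is not fully independent of the goal it is tested against, and its 5% level is not guaranteed. The likely effect is modest: 4.92% with the goal taken as fixed, and about 5.3%, 5.6% or 6.2% on average given 4/64 with 5, 10 or 19 overlapping subjects. Its direction in this study depends on an event count that the documents do not give.

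This rests on three assumptions: that the ABLATE AF trial and registry are one cohort; that the overlap lies between 0 and 19, which requires all 45 IDE subjects of Section 16.5 to be in the 64; and, for the averages, that overlapping subjects are a random draw from the 64. If the IDE safety cohort was larger than 45, the maximum overlap is below 19 and the average effect is smaller. The point calls for an inexpensive addition to the plan and does not invalidate the design.

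**What to change.** In Sections 16.2 and 16.4:
1. State how many PAS subjects were among the 64.
2. Keep the pooled exact binomial test as the primary safety analysis.
3. Pre-specify a repeat of that test excluding only those subjects, and report it beside the pooled result.
4. State that the safety conclusion will be qualified if the two differ.

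The cost is a few sentences and one extra analysis; the power of the pooled test is unchanged. The repeat has less power, about 75% with 19 excluded and 15% loss (315 evaluable), so it may miss the goal for want of numbers, and the wording of the qualification should allow for that. That loss of power is also the reason not to make the exclusion primary: it would take the main test below the planned 80%.

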6.3 Enrollment Procedures

All patients presenting with non paroxysmal (AF) and who are scheduled to undergo a primary open cardiac surgical procedure requiring cardiopulmonary bypass including valve surgery and/or CABG are potential study candidates for the ABLATE PAS. Potential patients will be pre-screened to confirm AF classification (persistent or longstanding persistent) for eligibility and offered the chance to participate in the study. Patients will not undergo any protocol specific assessments that are not considered to be standard of care prior to signing the informed consent form for the study. A Patient Screening Log will be provided to the study sites, in order to maintain a cumulative log of all screened patients. The reason for ineligibility will be documented on the study screening log including patients who refuse to participate in the study.

Each investigator will recruit subjects equitably in an effort to ensure to the best extent possible that the subject pool is representative in gender, race, ethnicity, and age of the population affected by the condition being studied.

[figure not shown]

6.4 Informed Consent Procedures

Informed consent must be obtained from a potential patient or their legally authorized representative prior to conducting any preoperative assessments that are not part of the routine preparation and evaluation of a patient for their scheduled open-heart procedure or evaluation of atrial fibrillation, even though the patient's eligibility has not yet been fully established. If during the course of the preoperative evaluations, a treatment patient is found not to be eligible for inclusion in the study, the patient or their representative should be notified and the reason for ineligibility documented on the screening log.

